15.5.4. Secondary Analysis

Secondary endpoints will be summarized by treatment group for the ITT and per-protocol cohorts based on the observed data and include the following summaries:

- Proportion of subjects achieving at least 7% and 10% TBL at 12 months;
- Percent TBL at 1 week, 1, 2, 4, 6, 9 and 12 months in the Treatment versus Control group;
- Percent EWL at 1 week, 1, 2, 4, 6, 9 and 12 months in the Treatment versus Control group;
- Proportion of subjects who achieve at least one obesity class reduction at 1 week, 1, 2, 4, 6, 9 and 12 months in the Treatment versus Control group;
- Change of BMI at 1 week, 1, 2, 4, 6, 9 and 12 months from baseline in the Treatment versus Control group;
- Change in weight-related quality of life at 1 week, 1, 2, 4, 6, 9 and 12 months as assessed by IWQOL-Lite Questionnaire in the Treatment versus Control group;
- Change in eating behavior at 1 week, 1 month and 12 months as assessed by the Eating Inventory;
- Change in appetite, hunger and fullness at 1 week, 1 month, 6 and 12 months as assessed by Visual Analog Scales in the Treatment versus Control group;
- Change in comorbid conditions and selected clinical parameters at 6 and 12 months in the Treatment group:
 - Prevalence of the metabolic syndrome and its individual components
 - Glucose, insulin, and insulin resistance (as estimated by HOMA)
 - High sensitivity C-reactive protein (hsCRP)
 - Lipid levels (LDL-C, HDL-C, and triglycerides)
 - Blood pressure
 - Waist circumference

The analysis of total body weight loss is described above. The other continuous and binary variables will be summarized descriptively by visit with 95% CIs presented for the mean values and proportions, respectively. For continuous endpoints, the change from baseline will be calculated if appropriate, and a t-test or a sign-rank test used to evaluate the null hypothesis that the change from baseline is centered around 0 (no change) within each treatment group. Treatment group comparisons for continuous endpoints will be made using mixed

models with post-hoc tests for each follow-up, and comparisons for qualitative variables will be made using Fisher's exact test, McNemar test or chi-square test, as appropriate.

The percent excess weight loss (%EWL) will be calculated as $(\text{Weight}(\text{kg})_{\text{BL}} - \text{Weight}(\text{kg})_{\text{FUP}}) / \text{ExcessWeight}(\text{kg})_{\text{BL}}$ where $\text{ExcessWeight}(\text{kg})_{\text{BL}}$ is calculated as difference between the subject's baseline weight in kilograms and the kilograms at which the subject's BMI would be 25.

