5. STUDY DESIGN

5.1. Study Design

This is a multicenter, prospective, randomized, parallel design, double-blinded, sham-controlled study. A total of 270 subjects are planned for the pivotal study cohort. Subjects meeting the general inclusion/exclusion criteria will undergo baseline endoscopic assessment. Those who meet endoscopic eligibility will be randomized in a 2:1 allocation to the Treatment or Control group stratified according to center. The Treatment group will receive the TPS placement and the Control group will receive a sham endoscopic procedure that does not include TPS placement.

Subjects will be followed up for 12 months after the index procedure or until the device is removed.

[figure not shown]
At 12 months, subjects in the Treatment group will undergo an endoscopic assessment followed by the TPS removal. Subjects in the Control group will complete all the same assessments as the Treatment group except the endoscopy.

Subjects who achieve a BMI of ≤ 22 kg/m² for two consecutive visits before the 12-months follow up will be considered a treatment success, have the device removed if in the Treatment group, and exit the study. A BMI of 22 kg/m² is selected as a reference value since it is a midpoint value of the normal BMI range, and a BMI ≥ 23 kg/m² has been shown to be associated with an increased risk of developing diabetes in the Nurses' Health Study that followed 43,581 women over 8 years.²⁸ The handling of these subjects in the analysis is described in Section 15.5.

Subjects in both groups will receive the same lifestyle modification education and counseling during the 12-month follow up duration. In brief, subjects will receive written instruction in lifestyle modification strategies for weight loss (e.g., caloric restriction, increasing physical activity, behavioral modification, etc.) at the beginning of the study. At each follow up visit, subjects will receive a brief (15 minute) lifestyle modification counseling performed by a medical provider (i.e., registered dietitian, nurse, behavioral health specialist)

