7.5. Patient Discontinuation

Once enrolled, each subject will remain in the study until the required follow-up period is complete. However, the subject has the right to withdraw from the study at any time without penalty or loss of benefit. The following events will result in terminating the subject's follow-up:

- Subject voluntary withdrawal
- Subject withdrawn by the Investigator as clinically indicated
- Subject becomes pregnant
- Subject lost to follow-up
- Subject death
- Study is terminated according to Section 5.6 (Early Study Termination)

In the case of subject withdrawal from the study, the TPS must be removed before the subject exits the study.

In case the TPS is removed early as described in Section 10.5, the subject's participation in the study is considered terminated. Any Adverse Events will be followed until resolution or stabilization according to Section 12.1.

In case a subject achieves normal BMI (≤ 22 kg/m²) for two consecutive visits before the 12-month follow up, the subject is considered to have completed the study. Subject will exit the study and the device should be removed in the treatment subjects.

A final endoscopy should be performed whenever possible before the Treatment subject exits the study.

The Sponsor must be notified of the reason for subject discontinuation. The site will document this information on the electronic case report form (eCRF) and make every effort to give a full description of the reason for withdrawal. Investigators must also report this information to the local IRB as defined by their institution's procedure.

Subjects who are terminated early will not be replaced by enrolling additional subjects.

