15.5.3. Primary Analysis

The %TBL will be calculated as $(\text{Weight}(\text{kg})_{\text{BL}} - \text{Weight}(\text{kg})_{\text{FUP}}) / \text{Weight}(\text{kg})_{\text{BL}}$. Where $\text{Weight}(\text{kg})_{\text{BL}}$ is the subject's weight at baseline in kilograms and $\text{Weight}(\text{kg})_{\text{FUP}}$ is the subject's weight at follow-up in kilograms.

The %TBL will be summarized at each follow-up visit through 12 months along with the observed total body weight at baseline and each follow-up visit by treatment group.

The testing of null hypotheses for the co-primary efficacy endpoints is described in Section 15.3.1.

In order to accommodate missing data in the primary effectiveness analyses, a multiple imputation approach will be used to impute missing follow-up weight observations. A total of 5 imputed samples will be created. Covariates (e.g., gender) will be used in the imputation procedure in addition to the subject's weight from previous visits. The multiple imputation approach was first described by Rubin.³⁵ The SAS procedures MI and MIANALYZE will be used to create the imputations and perform the analysis. The statistical null hypotheses for both co-primary endpoints will be tested on multiply imputed data sets. Sensitivity analyses will be done by evaluating the primary analysis on the ITT and CC cohorts. Further, a last observation carry forward (LOCF) imputation will be performed for the sensitivity purposes.

Additionally, the %TBL median, mean and standard deviation and percent of subjects with greater than 5%TBL will be summarized by treatment group and levels of covariates. Covariates include gender (male versus female), race (Caucasian versus non-Caucasian), age (\leq median, $>$ median), and baseline BMI (30-34.9 kg/m² and 35-40.0 kg/m²).

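### The 12-month obesity-class proportion, and on the plain reading the 7% and 10% weight-loss proportions, use observed data only, so early exits leave denominators that the imputed 5% co-primary keeps

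*Combined protocol and SAP*

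**What the plan says.** Section 15.5.4 (Secondary Analysis) begins: "Secondary endpoints will be summarized by treatment group for the ITT and per-protocol cohorts based on the observed data". The list that follows includes "Proportion of subjects achieving at least 7% and 10% TBL at 12 months" and "Proportion of subjects who achieve at least one obesity class reduction at 1 week, 1, 2, 4, 6, 9 and 12 months". No imputation or non-responder rule is given there. Qualitative variables are compared by Fisher's exact, McNemar or chi-square tests. After the list comes the sentence "The analysis of total body weight loss is described above", followed by the methods for the other continuous and binary variables.

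For the primary effectiveness analyses, section 15.5.3 states that "a multiple imputation approach will be used to impute missing follow-up weight observations", with five imputed samples, and that "The statistical null hypotheses for both co-primary endpoints will be tested on multiply imputed data sets". One of those endpoints is the proportion of Treatment subjects with at least 5% TBL, tested against 50% (15.3.1) in the per-protocol population (15.2). Early exit is not a stated ground for exclusion from that population. ITT is a sensitivity population for the primary endpoint.

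On exits, section 7.5 says: "In case the TPS is removed early as described in Section 10.5, the subject's participation in the study is considered terminated". Withdrawal also ends follow-up. Under section 5.1, subjects at BMI ≤22 kg/m² for two consecutive visits before month 12 "will be considered a treatment success, have the device removed if in the Treatment group, and exit the study". Section 5.1 refers to section 15.5 for how they are analysed.

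**The concern.** The 5%, 7% and 10% thresholds are cut points on one variable, the 12-month percent weight loss. Obesity class comes from the same weight and a fixed height. A reader will set these proportions side by side and expect them to describe the same subjects. Under the plain reading they do not: the 5% rate covers every per-protocol Treatment subject, while the 12-month secondary proportions cover only those with a 12-month weight.

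Several of the removal triggers in section 10.5 concern ulcer, pain or bleeding. Subjects who leave for such reasons may have lost less weight by month 12 than those who keep the device. If so, leaving them out raises the reported Treatment rate, and the ITT label hides that the table describes completers.

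**Working it through.** **Inputs.** Section 15.4 assumes mean %TBL of 13 (Treatment) and 5 (Control), SD 9, 243 evaluable subjects (162 + 81) and 270 enrolled (180 + 90).

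**The plan's own figures.** The standard error is 9 × √(1/162 + 1/81) = 1.225. A true difference of 8 against margins of 4 and 5 gives noncentrality 4/1.225 = 3.27 and 3/1.225 = 2.45. One-sided power at 0.025 (noncentral t) is 90.2% and 68.4%, against the stated 90% and 68.4%. The enrolment figure reproduces with 10% loss: 243/(1 − 0.10) = 270, the same fraction in each arm. These figures are sound and serve only as inputs.

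**Completer rates (normal, mean 13, SD 9).** P(≥c) = 1 − Φ((c − 13)/9):
- ≥7%: 1 − Φ(−0.667) = 74.8%
- ≥10%: 1 − Φ(−0.333) = 63.1%

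**Early exits.** The documents give neither the exit fraction f by reason nor the later weights of those who exit. I assume f = 10% (the plan's implied loss) or 20%, and a 12-month mean m of 3 to 8 with SD 9. For m = 3, P(≥7) = 32.8% and P(≥10) = 21.8%. For m = 8, they are 54.4% and 41.2%.

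**Rate over all Treatment subjects** = (1 − f) × completer rate + f × exit rate:

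| f | m | ≥7%, all | Gap from 74.8% | ≥10%, all | Gap from 63.1% |
|---|---|---|---|---|---|
| 10% | 3 | 70.6% | 4.2 | 58.9% | 4.1 |
| 10% | 8 | 72.7% | 2.0 | 60.9% | 2.2 |
| 20% | 3 | 66.4% | 8.4 | 54.8% | 8.2 |
| 20% | 8 | 70.7% | 4.1 | 58.7% | 4.4 |

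Gaps are in percentage points, from unrounded rates.

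As an outer bound at 10%, suppose all 18 of 180 exits are non-responders. The ≥7% rate falls from 121/162 = 74.7% to 121/180 = 67.2%, a gap of 7.5 points.

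**BMI ≤22 exits.** The loss needed is 1 − 22/30 = 26.7% from BMI 30 and 1 − 22/35 = 37.1% from BMI 35. Under mean 13 and SD 9, about 6.4% and 0.4% of Treatment subjects reach it, before two consecutive visits are required. Leaving these few subjects out would lower the responder rates, the opposite direction from the table.

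**The case against.** **The TBL proportions may already be imputed.** The sentence "The analysis of total body weight loss is described above", followed by methods for the other variables, can be read as sending the 7% and 10% proportions to 15.5.3. Against that, the opening sentence of 15.5.4 covers the whole list and 15.5.3 ties imputation to the primary effectiveness analyses. Both readings are open for 7% and 10%; obesity class is not a TBL variable and stays under the observed-data rule. That ambiguity is itself a reason to write the rule down.

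**Obesity class is reported by visit.** This stands. Early exits count until they leave, so the problem lies at visits after exit, including month 12.

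**A reader might infer that the protocol discards its own treatment successes.** The documents do not establish this. Section 5.1 places the handling of BMI ≤22 exits in section 15.5, and 15.5.6 and 15.5.7 are redacted. Section 14 links 15.5.6 to staged safety monitoring, but the content of 15.5.7 is unknown, so a rule cannot be called missing. The readable text does not score these subjects as responders in the 5% endpoint either.

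**A reader might infer that the between-arm comparison sets device-tolerant completers against nearly all Controls.** No passage says so. Section 15.4 inflates both arms by the same 10%, section 10.5 has Controls managed as if they carried the device, and withdrawal applies to both arms. The table above models Treatment only.

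**The endpoints do not decide the trial.** This also stands. Section 15.1 presents secondary results as an aid to interpretation and does not require their significance for study success.

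**Conclusion.** The inconsistency is real and should be corrected. It is clear for the 12-month obesity-class proportion and holds on the plain reading for the 7% and 10% TBL proportions. The 5% co-primary keeps early exits by imputation, within per-protocol Treatment subjects only; it is not a rate over all randomized subjects.

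At the plan's implied 10% loss, the observed Treatment rates are about 2-4 points too high; at an assumed 20%, about 4-8 points. These sizes rest on a normal distribution, on the planning mean and SD describing completers, and on exits averaging 3-8%. The direction reverses if most exits are BMI ≤22 successes, which the planning figures make unlikely. The effect on the between-arm difference is undetermined, because Control exits are not given.

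One might also expect contradictory results, with an observed ≥7% rate (74.8%) above the all-subject ≥5% rate. Among the cases tried, this occurs only at 20% exits with mean 3: 0.8 × 81.3% + 0.2 × 41.2% = 73.3%. At 20% with mean 5, the ≥5% rate is 75.0%. The comparison also uses a true rate, not the imputed rate the trial would report. It should not be presented as an expected result.

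**What to change.** In section 15.5.4, derive the 12-month ≥7%, ≥10% and obesity-class-reduction proportions, in both arms, from the multiply imputed 12-month weights for the full ITT and per-protocol cohorts, and combine them across imputations. State that this governs the 7% and 10% TBL proportions, so that the reference back to the TBL analysis is no longer ambiguous.

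Keep the observed-data proportions as supportive, labelled completers, with denominators by arm.

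Unless the redacted part of 15.5 already does so, state one rule for BMI ≤22 exits and apply it alike to the 5%, 7% and 10% endpoints, consistent with section 5.1. Scoring them as responders in the secondary endpoints alone would create a new mismatch with the co-primary.

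The cost is SAP wording and a little more analysis work. The imputations are already planned for the co-primary tests in both arms and for the ITT sensitivity analysis, and no new data or subjects are needed. The reported responder rates may be slightly less favourable. Imputation from earlier weights reduces the bias only as far as those weights predict month 12 after device removal, which is why the completers table should stay alongside.

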
Secondary Endpoints
	
 • Proportion of subjects who achieve at least 7% and 10% TBL at 12 months in the Treatment versus Control group • Percent total body weight loss over 12 months in the Treatment versus Control group • Percent excess weight loss over 12 months in the Treatment versus Control group • Proportion of subjects who achieve at least one obesity class reduction at 12 months in the Treatment versus Control group • Change of BMI over 12 months from baseline in the Treatment group • Change in weight-related quality of life over 12 months as assessed by IWQOL-Lite Questionnaire • Change in eating behavior over 12 months as assessed by the Eating Inventory • Change in appetite, hunger and fullness over 12 months as assessed by Visual Analog Scales • Change in comorbid conditions over 12 months in the Treatment group: 
 ○ Prevalence of the metabolic syndrome and its individual components ○ Glucose, insulin, and insulin resistance (as estimated by HOMA) ○ High sensitivity C-reactive protein (hsCRP) ○ Lipid levels (LDL-C, HDL-C, and triglycerides) ○ Blood pressure ○ Waist circumference

Safety Evaluation
	
Safety will be characterized through a summary of the incidence of adverse events. A Clinical Event Committee (CEC) will review and adjudicate all serious device-related adverse events and any other events deemed necessary.

Key Inclusion Criteria
	
 1. Male and female subjects between the ages of 22 to 60 2. A BMI between 30.0 to 40.0 kg/m² inclusive. Subjects with a BMI of 30.0 kg/m² to 34.9 kg/m² are required to have one or more of the following obesity-related mild-moderate comorbidities: 
 a. Type 2 Diabetes: meet one of the following criteria and currently not using insulin 
 i. HbA1c 6.5%-7.5% ii. Controlled, on stable dose of oral medications for at least 3 months b. Hypertension, meet one of the following criteria: 
 i. Arterial blood pressure >140 mmHg systolic or >90 mmHg diastolic on or off hypertensive medication ii. Arterial blood pressure ≤ 140 mmHg systolic and ≤ 90 mmHg diastolic on hypertensive medication c. Hyperlipidemia, meeting at least one of the following criteria: 
 i. Fasting blood total cholesterol level of ≥ 240 mg/dl ii. Fasting total triglyceride level of ≥ 200 mg/dl

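### The comorbidity endpoints are defined as change in the Treatment arm alone, which does not match the sham-controlled objective or the between-arm comparisons the plan already makes

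*Combined protocol and SAP*

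**What the plan says.** The synopsis gives the secondary endpoint as "Change in comorbid conditions over 12 months in the Treatment group", and Section 6.2 uses the same words. Section 15.5.4 repeats the restriction: "Change in comorbid conditions and selected clinical parameters at 6 and 12 months in the Treatment group".

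The surrounding text is comparative. Of the eight other bullets in 15.5.4, six name both arms, for example "Percent EWL at 1 week, 1, 2, 4, 6, 9 and 12 months in the Treatment versus Control group". The other two (the 7%/10% TBL proportions and the Eating Inventory) name no arm. Only the comorbidity bullet names Treatment alone.

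BMI shows the same label being corrected in one place but not the others. The synopsis and Section 6.2 have "Change of BMI over 12 months from baseline in the Treatment group"; Section 15.5.4 has "Change of BMI at 1 week, 1, 2, 4, 6, 9 and 12 months from baseline in the Treatment versus Control group".

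The general text of 15.5.4 covers both kinds of analysis. It opens with "Secondary endpoints will be summarized by treatment group for the ITT and per-protocol cohorts based on the observed data". Its closing paragraph has a t-test or signed-rank test "used to evaluate the null hypothesis that the change from baseline is centered around 0 (no change) within each treatment group", and then states "Treatment group comparisons for continuous endpoints will be made using mixed" models. Fisher, McNemar or chi-square tests are listed for qualitative variables. No endpoint is exempted from the between-arm comparison.

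**The concern.** Section 4 frames the trial as a comparison with sham and then lists comorbidity change among the secondary endpoints, with no restriction to one arm. A change from baseline in the Treatment arm combines any device effect with everything both arms share: identical counseling (Section 5.1), repeated visits and regression to the mean. The plan itself expects the shared part to be non-zero. Section 15.4 assumes 5% weight loss on sham, and Section 2.2 says that a loss of 3% can improve some cardiovascular risk factors.

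Section 15.5.4 therefore plans two results for each marker, a within-arm test against zero and a between-arm comparison, and the endpoint label points to the first. A report that presented a significant Treatment change as the endpoint result would be consistent with the definition, yet would say nothing specific about the device. The ambiguity is sharper for metabolic syndrome prevalence, because McNemar's test, one of the listed options, is a paired test and could be run in Treatment alone.

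**Working it through.** **1. The definitions side by side**

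| Endpoint | Synopsis | Section 6.2 | Section 15.5.4 |
|---|---|---|---|
| Comorbid conditions | Treatment only | Treatment only | Treatment only |
| BMI change | Treatment only | Treatment only | Treatment versus Control |
| %EWL | Treatment versus Control | Treatment versus Control | Treatment versus Control |

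The comorbidity endpoints are the only ones still single-arm in the analysis section.

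**2. The plan's own figure**

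No power or precision is stated for the comorbidity endpoints. The evaluable numbers used below (162 Treatment, 81 Control) come from Section 15.4, so I checked that section first. With a difference of 8, margin 4, SD 9 and one-sided alpha 0.025, the noncentrality is (8 − 4) / (9 × √(1/162 + 1/81)) = 4 / (9 × 0.1361) = 3.27. Power on 241 df is 90.2%, against 90% stated. The figure reproduces.

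**3. What the labelled quantity does when the device has no effect**

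Assumptions: both arms shift by the same amount *d*, in units of the SD of the change; normal data; two-sided alpha 0.05. The documents give neither *d* nor an SD for any of these markers, so *d* is varied.

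- Within-arm test: one-sample t with n − 1 df and noncentrality *d*√n. For Treatment with *d* = 0.2 this is 0.2 × √162 = 2.55, which gives 71.6%.
- Between-arm test: two-sample t, 162 versus 81. The true difference is 0.
- The between-arm and joint probabilities come from 20,000 simulated trials per value of *d*.

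| Common shift *d* | Treatment within-arm significant | Sham within-arm significant | Between-arm significant | Treatment improved significantly, between-arm not significant |
|---|---|---|---|---|
| 0.1 | 24.4% | 14.4% | 5.3% | 22.7% |
| 0.2 | 71.6% | 42.8% | 5.0% | 68.8% |
| 0.3 | 96.7% | 76.0% | 4.9% | 92.4% |
| 0.4 | 99.9% | 94.5% | 5.1% | 94.8% |
| 0.56 (5/9) | 100.0% | 99.9% | 5.0% | 95.0% |

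The last row uses the plan's sham assumption for %TBL (mean 5, SD 9). It is an analogy only, since nothing in the documents transfers that ratio to lipids, hsCRP or blood pressure. With 180 Treatment subjects the within-arm rates at *d* = 0.1 to 0.3 become 26.6%, 76.1% and 98.0%.

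**4. What the between-arm result would deliver**

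The 95% CI half-width for the difference in change is t(0.975, 241) × √(1/162 + 1/81) = 1.970 × 0.1361 = 0.268 SD of the change.

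If the baseline value is added as a covariate, and baseline and 12-month variances are equal with correlation *r*, the ratio of the adjusted half-width to that of an unadjusted change score is √((1 + r)/2). For *r* = 0.3, 0.5 and 0.7 (assumed) this is 0.806, 0.866 and 0.922, so the interval is about 19%, 13% or 8% narrower.

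**The case against.** The strongest reply is that the wanted analysis is already in the plan. Section 15.5.4 summarizes every secondary endpoint by arm and compares the arms without exemption, so a Treatment-only report would depart from it. The bullets are introduced as summaries and use comparators loosely elsewhere too. Section 4's comparison with sham is worded around weight reduction, and its sentence on comorbidities names no comparator. Because within-arm tests are run in both arms, the tables would also show sham improving: at *d* = 0.4, sham is significant 94.5% of the time.

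Much of this stands, and it is why the point is minor. No analysis is missing and no error rate of the between-arm test is wrong. The shift sizes are assumed; at *d* = 0.05 the Treatment within-arm test is significant only about 10% of the time. Enrolling subjects with controlled comorbidities, and adjusting their medication as weight falls, could keep shifts small. The covariate gain is relative to an unadjusted change-score model, which the plan does not specify, and it is a precision benefit rather than a correction.

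The definition itself remains unanswered. Three sections name a single-arm quantity as the endpoint, and no sentence says which of the two planned results is the endpoint result. Seeing sham improve as well does not replace an estimate of the difference: at *d* = 0.2, Treatment is significant and sham is not in about 41% of trials, partly because the Treatment arm is twice as large.

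**Conclusion.** The concern holds, as a minor point. The comorbidity endpoints are defined in all three places as an uncontrolled change in the Treatment arm, and this conflicts with the design and with the comparisons 15.5.4 plans. With no device effect and a common improvement of 0.1 to 0.4 SD, the labelled quantity would be significant while the between-arm comparison is not in 23% to 95% of trials. That range illustrates the label taken literally, rests on assumed shifts, and is not an error rate of the planned between-arm analysis. Under Section 15.1, tests of secondary endpoints only aid interpretation and are not needed for success; sample size, alpha and the success criteria are unaffected. The conclusion about the wording depends on none of the assumed values.

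**What to change.** 1. In the synopsis, Section 6.2 and Section 15.5.4, define the comorbidity endpoints as Treatment versus Control. Do the same for BMI change in the synopsis and Section 6.2, where it still differs from 15.5.4.
2. Add one sentence to 15.5.4: the Treatment minus Control difference at 6 and 12 months, with its 95% CI, is the endpoint result, and within-arm tests (t-test, signed-rank, McNemar) are descriptive.
3. Include the baseline value as a covariate in the planned mixed model. A baseline-adjusted model for metabolic syndrome prevalence is optional.

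The cost is wording in three sections, one sentence and one model term. No visits, samples or subjects are added: Control subjects have the same assessments apart from endoscopy (Section 5.1), and fasting blood is drawn at baseline, 6 and 12 months (Section 11.4). The one thing given up is presenting within-arm significance as a device effect.

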6.2. Secondary Effectiveness Endpoints

The following secondary endpoints will be assessed in this study:

- Proportion of subjects who achieve at least 7% and 10% TBL at 12 months in the Treatment versus Control group
- Percent total body weight loss over 12 months in the Treatment versus Control group
- Percent excess weight loss over 12 months in the Treatment versus Control group
- Proportion of subjects who achieve at least one obesity class reduction at 12 months in the Treatment versus Control group
- Change of BMI over 12 months from baseline in the Treatment group
- Change in weight-related quality of life over 12 months as assessed by IWQOL-Lite Questionnaire
- Change in eating behavior over 12 months as assessed by the Eating Inventory
- Change in appetite, hunger and fullness over 12 months as assessed by Visual Analog Scales.
- Change in comorbid conditions over 12 months in the Treatment group:
 - a) Prevalence of the metabolic syndrome and its individual components
 - b) Glucose, insulin, and insulin resistance (as estimated by HOMA)
 - c) High sensitivity C-reactive protein (hsCRP)
 - d) Lipid levels (LDL-C, HDL-C, and triglycerides)
 - e) Blood pressure
 - f) Waist circumference

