15. STATISTICAL DESIGN AND ANALYSIS

15.1. Statistical Overview

Data will be summarized by the number, mean, median, standard deviation and range for continuous variables and by number and relative frequency for categorical variables. Summaries will be presented by treatment group and visit as appropriate. A summary of the subjects combined will be provided for the baseline information only. Missing data imputation approaches are outlined below.

The alpha level will be set to 0.05 based on the two-sided testing and 0.025 for the one-sided approach, if not explicitly stated otherwise. Study success criteria are defined in Section 15.3.1. Statistical testing and confidence intervals for sensitivity analyses and secondary endpoints will be presented as an aid in interpreting study results, but statistical significance is not required for study success. Unless otherwise indicated, all statistical inferences will be based on two-sided 95% confidence intervals and p-values less than or equal to 0.05 will be considered significant.

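### Section 15.5.4 names no baseline covariate in the mixed models that compare the arms on continuous secondary endpoints; adding one is a free gain in precision

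*Combined protocol and SAP*

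**What the plan says.** The between-arm method for continuous secondary endpoints is one sentence in Section 15.5.4: "Treatment group comparisons for continuous endpoints will be made using mixed", continuing "models with post-hoc tests for each follow-up". It names no covariate, response scale or covariance structure.

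Baseline appears in the sentence before, which deals with tests within each arm: "the change from baseline will be calculated if appropriate, and a t-test or a sign-rank test used to evaluate the null hypothesis" of no change. Summaries are to be "summarized descriptively by visit with 95% CIs presented for the mean values and proportions, respectively". Section 15.1 adds other statistics: "Data will be summarized by the number, mean, median, standard deviation and range for continuous variables".

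The arm scope differs by endpoint:
- In 15.5.4 the changes in BMI, IWQOL-Lite and VAS are marked as Treatment against Control. (Section 6.2 limits BMI change to the Treatment group and gives no arm for the other two.)
- The Eating Inventory bullet names no arm, so only the general mixed-model sentence reaches it.
- hsCRP, insulin, HOMA and triglycerides fall under "Change in comorbid conditions and selected clinical parameters at 6 and 12 months in the Treatment group". Section 6.2 agrees: "Change in comorbid conditions over 12 months in the Treatment group".

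Baseline collection is scheduled in Sections 11.4 (fasting bloods), 11.5 (VAS, Eating Inventory), 11.7 (IWQOL-Lite) and 11.9.2 (weight and BMI). Section 11.9.2 also waives the baseline visit when screening falls within 7 days of the procedure and lets screening data stand in. Section 11.9.1 and Appendix B schedule none of the three questionnaires at screening.

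**The concern.** In a randomised comparison, conditioning on the baseline value gives a between-arm estimate at least as precise as comparing change scores or follow-up levels, apart from one degree of freedom. It also removes the part of any chance baseline imbalance that predicts follow-up. Subtracting baseline fixes its coefficient at 1; ignoring it fixes the coefficient at 0; a covariate lets the data choose.

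The comparisons affected are the trial's between-arm evidence on quality of life and eating behaviour, with about 81 evaluable Controls. Intervals wider than they need be are harder to interpret, and leaving the model unstated leaves its form to be settled after data are in hand. For right-skewed laboratory markers the response scale would matter too, but only if those markers are to be compared with Control.

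**Working it through.** **1. The plan's own figures.** Section 15.4 gives no SD, correlation or power for any secondary endpoint. Its evaluable numbers (162 Treatment, 81 Control) come from the first co-primary endpoint, and its power there reproduces:
- SE = 9 × √(1/81 + 1/162) = 1.225.
- 4% margin: (8 − 4)/1.225 − 1.960 = 1.306, power 90.4% (90.2% by noncentral t; stated 90%).
- 5% margin: 68.8% (68.4% by noncentral t; stated 68.4%).

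Neither figure depends on the secondary models.

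**2. Baseline covariate.** Let ρ be the correlation between baseline and follow-up, with equal variances σ² at both times. Per-arm variance at one visit, in units of σ²:
- follow-up level: 1
- change score: 2(1 − ρ)
- baseline as covariate: 1 − ρ²

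The variance ratio against change is (1 − ρ²)/[2(1 − ρ)] = (1 + ρ)/2; against level it is 1 − ρ². The SE cut is 1 minus the square root of the ratio. At ρ = 0.5 both ratios are 0.75, so the cut is 1 − 0.866 = 13%, and a change-score analysis would need 243/0.75 = 324 subjects to match, 33% more. A test with 80% power on change scores has noncentrality 1.960 + 0.842 = 2.802. With the covariate this becomes 2.802/0.866 = 3.235, giving 89.9% power.

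| ρ (assumed) | Ratio vs change | SE cut vs change | Ratio vs level | SE cut vs level | N a change analysis needs to match 243 | Power where change has 80% |
|---|---|---|---|---|---|---|
| 0.3 | 0.65 | 19% | 0.91 | 5% | 374 | 93.5% |
| 0.5 | 0.75 | 13% | 0.75 | 13% | 324 | 89.9% |
| 0.7 | 0.85 | 8% | 0.51 | 29% | 286 | 86.0% |
| 0.8 | 0.90 | 5% | 0.36 | 40% | 270 | 84.0% |
| 0.9 | 0.95 | 3% | 0.19 | 56% | 256 | 82.0% |

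**3. Skewed markers, only if compared with Control.** Lognormal data were simulated for 162 against 81, one follow-up visit, two-sided 0.05, 2,000 trials per setting. The effect in each row was set so that a log-scale, baseline-adjusted analysis has about 80% power. Log-SD and ρ are assumed.

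| Log-SD | ρ | Raw change | Raw, baseline-adjusted | Log, baseline-adjusted |
|---|---|---|---|---|
| 0.4 | 0.5 / 0.7 | 61 / 65% | 77 / 74% | 81 / 79% |
| 0.6 | 0.5 / 0.7 | 51 / 58% | 69 / 71% | 78 / 80% |
| 0.8 | 0.5 / 0.7 | 42 / 47% | 65 / 62% | 79 / 80% |
| 1.0 | 0.5 / 0.7 | 38 / 37% | 59 / 52% | 79 / 80% |

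The last two columns isolate the effect of scale. It is 3 to 5 points at log-SD 0.4 and 20 to 28 points at log-SD 1.0. For a fixed 25% reduction (also assumed), raw-change power is already 93 to 99% at log-SD 0.5, so little is left to gain. At log-SD 0.9 it is 38 to 54%, against 78 to 90% for the log scale with baseline.

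**The case against.** **Silence is not exclusion.** A reader might infer that the models use no baseline value at all. The text does not support that: change from baseline is calculated where appropriate, so baseline can enter by subtraction, and nothing rules out a covariate. A mixed model with baseline as a repeated response and a common baseline mean would recover most of the gain. This stands as a correction to the stronger reading. It does not remove the point, because neither form is specified, and a change score without the covariate is one of the two comparators in the table.

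**The skewed markers are not clearly in scope.** A reader might also infer that hsCRP, insulin, HOMA and triglycerides are to be compared between arms as raw means. Both endpoint lists confine them to the Treatment group. The general mixed-model sentence could be read to cover them, and Section 4 frames the trial as a comparison with sham, but no such comparison is clearly planned. The raw scale is likewise inferred from silence and from the summary wording; medians and ranges are also reported, and a signed-rank test is available within arm. The second table therefore describes a conditional loss, not one the plan commits to.

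**Low consequence.** Unadjusted comparison of change is valid in a randomised trial. Section 15.1 treats secondary tests as an aid to interpretation and does not require their significance for success. Both points are correct and limit the weight of this one.

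**Baselines may be missing.** Subjects covered by the waiver in Section 11.9.2 may have no questionnaire baseline. Change scores would lose them too, but a covariate model needs a stated rule.

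**Conclusion.** The point holds for the baseline covariate and is a free improvement. Run as written, on change or on level, the between-arm comparisons of BMI, IWQOL-Lite and VAS (and of the Eating Inventory, if the general sentence is meant to reach it) are less precise than the scheduled data allow. The standard error would fall by 19, 13 or 8% against change scores, and by 5, 13 or 29% against levels, at correlations of 0.3, 0.5 or 0.7; at 0.9 the gain over change scores is about 3%. These sizes rest on assumed correlations and equal variances, since the documents give neither.

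For hsCRP, insulin, HOMA and triglycerides the first question is whether they are compared with Control at all. Any gain from the log scale depends on that answer and on assumed log-SDs, and is small for markers of modest spread. No stated power or sample size changes, and the success criterion is untouched.

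**What to change.** In Section 15.5.4, before unblinding:

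1. For each between-arm mixed model, specify arm, visit, arm by visit, baseline value and baseline by visit, and name the endpoints covered, including whether the Eating Inventory is one.
2. State how subjects whose baseline visit was waived under Section 11.9.2, and who may lack questionnaire baselines, are handled. One option is to model baseline as a repeated response with a common mean across arms, which keeps them in the analysis.
3. State whether the markers listed for the Treatment group only are compared with Control. If so, analyse hsCRP, insulin, HOMA and triglycerides on the log scale with log baseline as covariate, and report ratios of geometric means with 95% CIs.

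The cost is SAP wording, plus a line in the report explaining ratios of geometric means. No new visits, measurements or subjects are needed.
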